5.4.8. Study Stopping Rules and Patient Discontinuation

If the incidence of all bleeding events (all Grades) that are related to PF-06952229 is observed above 25%, the trial will be suspended.

All Grade 3 or Grade 4 bleeding events that are related to PF-06952229 will result in trial discontinuation for any patient who experience such clinical findings.

Any subsequent Grade 3 or Grade 4 bleeding event that is related to PF-06952229 will trigger a full review of overall safety of PF-06952229 and an assessment of the benefit/risks of this molecule in the studied patient population.

5.5. Investigational Product Storage

The investigator, or an approved representative, eg, pharmacist, will ensure that all investigational products, including any marketed products, are stored in a secured area with controlled access under required storage conditions and in accordance with applicable regulatory requirements.

Investigational products should be stored in their original containers and in accordance with the labels.

Any storage conditions stated in the SRSD will be superseded by the storage conditions stated on the product label.

Site systems must be capable of measuring and documenting (for example, via a log), at a minimum, daily minimum and maximum temperatures for all site storage locations (as applicable, including frozen, refrigerated, and/or room-temperature products). This should be captured from the time of investigational product receipt throughout the study. Even for continuous-monitoring systems, a log or site procedure that ensures active evaluation for excursions should be available. The intent is to ensure that the minimum and maximum temperature is checked each business day to confirm that no excursion occurred since the last evaluation and to provide the site with the capability to store or view the minimum/maximum temperature for all nonworking days upon return to normal operations. The operation of the temperature monitoring device and storage unit (for example, refrigerator), as applicable, should be regularly inspected to ensure they are maintained in working order.

Any excursions from the product label storage conditions should be reported to Pfizer upon discovery. The site should actively pursue options for returning the product to the storage conditions described in the labeling, as soon as possible. Deviations from the storage requirements, including any actions taken, must be documented and reported to Pfizer.

Once an excursion is identified, the investigational product must be quarantined and not used until Pfizer provides permission to use the investigational product. It will not be considered a protocol deviation if Pfizer approves the use of the investigational product after the temperature excursion. Use of the investigational product prior to Pfizer approval will be considered a protocol deviation.

Specific details regarding information the site should report for each excursion will be provided to the site.

Receipt of materials, door opening and closing, and other routine handling operations where the products are briefly out of the temperature range described in the labeling are not considered excursions.

Site staff will instruct patients on the proper storage requirements for take home investigational products.

5.6. Investigational Product and Study Treatment Accountability

The investigator site must maintain adequate records documenting the receipt, use, loss, or other disposition of the investigational product and study treatment supplies. All investigational products and study treatment will be accounted for using a drug accountability form/record. All bottles of study treatments must be returned to the investigator by the patient at every visit and at the end of the trial.

5.6.1. Destruction of Investigational Product Supplies

The sponsor or designee will provide guidance on the destruction of unused investigational product (eg, at the site). If destruction is authorized to take place at the investigator site, the investigator must ensure that the materials are destroyed in compliance with applicable environmental regulations, institutional policy, and any special instructions provided by Pfizer, and all destruction must be adequately documented.

5.7. Concomitant Treatment(s)

Concomitant treatment considered necessary for the patient's well-being may be given at discretion of the treating physician (including bisphosphonates or approved RANK ligand (RANK-L) targeted agents (for example, denosumab).

All concomitant treatments, blood products, as well as nondrug interventions received by patients from screening until the end of study visit will be recorded on the CRF.

Anticoagulation therapy with heparin, low molecular weight heparin, vitamin K antagonists, anti platelet agents, or factor Xa inhibitors is prohibited throughout the study and for at least 28 days post the last dose of study treatment. If anticoagulation therapy is medically indicated on trial, patients should stop treatment with PF-06952229. For those requiring temporary anticoagulant therapy, resumption of PF-06952229 treatment may be permitted after discussion with the Sponsor. In any other case, study treatment should be permanently discontinued, and the patient should enter the follow-up portion of the trial.

Because inhibition of CYP3A4/5 isoenzymes may increase PF-06952229 exposure leading to potential increases in toxicities, the use of known strong and moderate inhibitors are not permitted within 10 days or 5 half-lives of the CYP3A4/5 inhibitors, whichever is longer prior to the first dose of PF-06952229. A list of CYP3A4/5 inhibitors is provided in Appendix 9.

Because induction of CYP3A4/5 isoenzymes may decrease PF-06952229 exposure leading to potential decrease in efficacy, the use of strong or moderate CYP3A4/5 inducers is not permitted within 10 days or 5 half-lives of CYP3A4/5 inducers, whichever is longer prior to the first dose of PF-06952229. A list of CYP3A4/5 inducers is provided in Appendix 9.

5.7.1. Proton-Pump Inhibitors

Acid reducing agents (ARAs) may decrease PF-06952229 absorption and exposure. The potential impact to absorption and exposure may be the greatest with proton pump inhibitors (PPIs). When possible patients who are currently taking PPIs should be switched to antacids

or H2-Receptor antagonists (see below) at least 14 days prior to Cycle 1 Day 1 and continue with these alternative ARAs throughout the study.

In Part 1A, Part 1B, and Part 2B, if the patient starts the study treatment period currently taking a PPI, the dose and frequency should be recorded in the appropriate CRF page and the patient should maintain this treatment until after Cycle 2 Day 1 visit, to allow for more accurate estimation of the impact of enzalutamide (Part 1B, and Part 2B) on PF-06952229 exposure. If the patient stops or alters treatment with PPI during this period, this should be recorded in the CRF.

5.7.2. Antacids or H2-Receptor Antagonists

Recommendations about the use of antacids or H2-receptor antagonists and PF-06952229 dosing include the following (but are not limited to): cimetidine, famotidine, nizatidine, ranitidine. If needed, administer H2-receptor antagonists with a staggered dosing regimen (twice daily). The dosing of PF-06952229 should occur at least 10 hours after H2-receptor antagonist evening dose and 2 hours before the H2-receptor antagonist morning dose. However, if needed, local antacids should be given at least 2 hours before or at least 2 hours after PF-06952229 administration.

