Appendix 9. Prohibited Concomitant Medications Which May Result in Drug-Drug Interaction (DDI)

This is not an all-inclusive list. Study personnel should stay current and consult with their pharmacy to exclude all concomitant medications that are CYP3A4/5 inhibitors or inducers.

Drug Category	Drugs or Supplement	Required Washout Period
Drug Guergery	a supplement	Requirement
CYP3A4/3A5	VIEKIRA PAK	10 days
Inhibitor	Anti-HIV retroviral drugs	or
	containing ritonavir	5 half-lives
	ritonavir	whichever is longer
	cobicistat	
	troleandomycin	
	telaprevir	
	itraconazole	
	indinavir	
	voriconazole	
	mifepristone	
	mibefradil	
	clarithromycin	
	posaconazole	
	telithromycin	
	grapefruit juice	
	ceritinib	
	conivaptan	
	nefazodone	
	nelfinavir	
	saquinavir	
	ribociclib	
	idelalisib	
	boceprevir	
	Erythromycin	
	Fluconazole	
	Atazanavir	
	Darunavir	
	Duvelisib	
	Diltiazem	
	Dronedarone	
	Crizotinib	
	Fedratinib	
	Letermovir	
	Aprepitant	
	Lefamulin	
	Casopitant	
	Amprenavir	
	Faldaprevir	
	Imatinib	
	Verapamil	

Drug Category	Drugs or Supplement	Required Washout Period
		Requirement
	Ravuconazole	
	Netupitant	
	Nilotinib	
	Istradefylline	
	Tofisopam	
	Cyclosporine	
	Ciprofloxacin	
	Voxelotor	
	Isavuconazole	
	Cimetidine	
	fluvoxamine	
CYP3A4/3A5	carbamazepine	10 days
Inducer	enzalutamide	or
	rifampicin	5 half-lives
	mitotane	whichever is longer
	avasimibe	
	rifapentine	
	apalutamide	
	ivosidenib	
	phenytoin	
	St John's Wort extract	
	phenobarbital	
	semagacestat	
	efavirenz	
	dabrafenib	
	cenobamate	
	lesinurad	
	bosentan	
	thioridazine	
	rifabutin	
	Lorlatinib	
	Nafcillin	
	talviraline	
	lopinavir modafinil	
	etravirine	
	elagolix	
	lersivirine	
	telotristat ethyl	
	terourstat euryr	

Note 1: Half-life refers to the half-life of the parent drug and its metabolites, which are inhibitors or inducers. The longest half-life should be used to calculate the period necessary to washout a medication prior to the first dose of study treatment.

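### Section 5.7.2 names cimetidine as a usable H2-receptor antagonist, while Appendix 9 prohibits it by name as a CYP3A4/3A5 inhibitor

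*Protocol*

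**What the plan says.** Three parts of the protocol bear on this.

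- **Section 5.7.1** warns that "Acid reducing agents (ARAs) may decrease PF-06952229 absorption and exposure" and asks that proton-pump inhibitor users be moved, when possible, to an antacid; the sentence goes on: "or H2-Receptor antagonists (see below) at least 14 days prior to Cycle 1 Day 1 and continue with these alternative ARAs throughout the study".
- **Section 5.7.2** is the text that follows: "Recommendations about the use of antacids or H2-receptor antagonists and PF-06952229 dosing include the following (but are not limited to): cimetidine, famotidine, nizatidine, ranitidine". It then tells sites, if an H2-receptor antagonist is needed, to give it on a staggered twice-daily regimen. PF-06952229 is taken at least 10 hours after the evening dose and 2 hours before the morning dose. Nothing sets cimetidine apart from the other three.
- **Appendix 9** carries a title declaring its contents prohibited. It names cimetidine in the CYP3A4/3A5 inhibitor block, between isavuconazole and fluvoxamine, and requires a washout of 10 days or 5 half-lives, whichever is longer. Its introduction says: "Study personnel should stay current and consult with their pharmacy to exclude all concomitant medications that are CYP3A4/5 inhibitors or inducers".

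Section 5.7 and exclusion criterion 30 both send the reader to Appendix 9 for the inhibitor list. Section 5.7 gives the reason for the restriction: "Because inhibition of CYP3A4/5 isoenzymes may increase PF-06952229 exposure leading to potential increases in toxicities".

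**The concern.** Site staff get conflicting guidance on one named drug. Someone managing a patient's acid suppression will read Sections 5.7.1 and 5.7.2, find cimetidine first in the list and follow the spacing rule. Someone checking the same patient against Appendix 9 will find a prohibited drug inside its washout. No text says which governs.

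The protocol itself supplies the reason to care. Section 1.2.4 gives CYP3A4 metabolism as the primary clearance route (fraction about 0.9) and anticipates significant exposure changes with strong CYP3A4 inhibitors. Section 5.7 ties inhibition to possible added toxicity. In a first-in-patient dose-finding study, an unplanned change in exposure is something the concomitant-medication rules are meant to prevent.

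**Working it through.** The plan states no figure to reproduce, so the check is a comparison of texts, a count and a timing argument.

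**1. Is the same drug in both places?** The H2-receptor antagonists named in Section 5.7.2, compared with the Appendix 9 inhibitor block (51 entries as extracted):

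| Agent in Section 5.7.2 | In the Appendix 9 inhibitor block? |
|---|---|
| cimetidine | yes |
| famotidine | no |
| nizatidine | no |
| ranitidine | no |

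Matches: 1 of 4 = 25%. Appendix 9 says it is not all-inclusive, so the other three still fall under its pharmacy check.

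**2. Does following Sections 5.7.1 and 5.7.2 breach the washout?**

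- Required drug-free interval before first dose: W = max(10 days, 5 × half-life). Hence W ≥ 10 days = 240 hours, whatever the half-life. The documents give no half-life for cimetidine.
- Section 5.7.1 has the agent started at least 14 days before Cycle 1 Day 1 and continued. It is therefore in use at first dose.
- Under the twice-daily staggering in Section 5.7.2, the last dose before Cycle 1 Day 1 falls on the evening before. The stated minimum gap is 10 hours.
- A gap from one evening to the next day's dose is far short of 240 hours. The washout is breached.

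**3. Is cimetidine exempted anywhere?** No exempting text was found in Section 5.7, 5.7.1, 5.7.2, exclusion criterion 30 or Appendix 9.

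**4. How far does the restriction reach?**

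- *Strength.* Exclusion criterion 30 and Section 5.7 restrict strong and moderate inhibitors, and the documents do not grade cimetidine. A breach of those two texts is therefore not established. Appendix 9 has no strength tiers, applies its washout to every listed inhibitor, and tells sites to exclude all CYP3A4/5 inhibitors.
- *Period.* Section 5.7 and Note 1 to Appendix 9 state only a window before first dose; Note 1 reads "The longest half-life should be used to calculate the period necessary to washout a medication prior to the first dose of study treatment". A ban during treatment has to be inferred. Support for it comes from the Appendix 9 title and instruction, and from criterion 30 covering anticipated as well as current need. Section 4.3 also bars grapefruit products until the end of study or discontinuation, and grapefruit juice is an Appendix 9 inhibitor. Appendix 8 tells sites to go on considering the Section 5.7 interactions during treatment, but only for drugs given for SARS-CoV2. The conflict shown in step 2 does not need this inference.

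**5. Can an effect on exposure be computed?** No. Inhibition would push PF-06952229 exposure up, while Section 5.7.1 says acid reduction may lower it. Neither the size nor the net direction follows from the documents.

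**The case against.** The strongest case is that this is loose drafting rather than contradiction. Section 5.7.2 gives a spacing rule for a drug class, concerned with absorption, and never says outright that cimetidine is permitted. Appendix 9 concerns metabolism. A careful reader could apply both by avoiding listed drugs and spacing the rest. That reading is possible, but naming cimetidine first and then explaining how to give H2-receptor antagonists invites its use.

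A second argument is that Appendix 9 cannot be an absolute ban, because it also lists enzalutamide, which is given daily in Parts 1B and 2B. Enzalutamide, however, is an assigned study drug with its own dosing text in Sections 3.1.1.5 and 5.4.3. Cimetidine has no such override.

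A third is that Appendix 9 may be the text in error, since the body of the protocol restricts only strong and moderate inhibitors. The documents cannot settle this. It bears on which text to change, not on whether the two disagree.

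What stands is that the practical reach is small. The problem arises only when a patient needs acid suppression and is given cimetidine in particular. Written sponsor permission before dosing (Section 5.1), the Appendix 9 pharmacy check, CRF recording of concomitant treatments (Section 5.7) and ongoing safety discussions (Section 9.7) may catch it. Section 9.1 does not name CYP3A inhibitor use as a major treatment deviation, so nothing shows that a patient would be lost from the MTD-evaluable set. None of these safeguards tells a site which instruction to follow.

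**Conclusion.** The concern holds. As written, a site that chooses cimetidine under Section 5.7.2 on the Section 5.7.1 timing breaches the Appendix 9 washout, for any half-life. The conflict covers one optional agent of four, and a site can comply with every section by using another listed agent or an antacid.

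The conclusion rests on reading the Appendix 9 washout as applying to each inhibitor it lists, which is how its table is laid out. It does not rest on any assumed inhibitory strength for cimetidine or on a ban during treatment. The demonstrated consequence is an avoidable protocol deviation; no effect on DLT or PK results is shown. Because this is an operative instruction to sites and the protocol gives a toxicity reason for the restriction, it should be corrected.

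**What to change.** Delete cimetidine from the list in Section 5.7.2 and add a sentence there: H2-receptor antagonists listed in Appendix 9 must not be used. Famotidine, nizatidine, ranitidine and antacids remain available. Changing Section 5.7.2 rather than Appendix 9 is the cautious direction, given the toxicity reason stated in Section 5.7. The cost is one drug name removed and one sentence added, with no new data, visits or patients.

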5.8. Other Anti-tumor/Anti-Cancer or Experimental Drugs

No additional anti-tumor treatment will be permitted while patients are receiving study treatment. Additionally, the initiation of new concurrent vitamins or herbal supplements is not permitted unless discussed and agreed with the sponsor.

Palliative radiotherapy on study is permitted for the treatment of painful bony lesions provided that the lesions were known at the time of study entry and the investigator clearly indicates that the need for palliative radiotherapy is not indicative of disease progression. In view of the current lack of data about the interaction of PF-06952229 with radiotherapy, PF-06952229 treatment should be interrupted during palliative radiotherapy, stopping 14 days before and resuming treatment after recovery to baseline.

5.9. Supportive Care

Palliative and supportive care for disease related symptoms may be administered at the investigator's discretion and according to any available American Society of Clinical Oncology (ASCO) guidelines.

Patients currently being treated with a gonadotropin-releasing hormone agonist (GnRH agonist) may continue treatment while on clinical study C3881001 as long as the GnRH agonist treatment has been well tolerated for at least 3 months prior to study entry. If patients have had tolerability issues with GnRH agonists, such patients may be allowed to enroll with agreement of the Pfizer medical monitor.

5.9.1. Hematopoietic Growth Factors

Primary prophylactic use of granulocyte-colony stimulating factors is not permitted during the first 14 days of Cycle 1, but they may be used to treat treatment emergent neutropenia as

indicated by the current American Society of Clinical Oncology guidelines or the relevant full prescribing information for the growth factor.

Erythropoietin or other erythropoiesis stimulating agents (ESAs) may be used at the investigator's discretion for the supportive treatment of anemia as described in current American Society of Clinical Oncology/American Society of Hematology guidelines or the relevant full prescribing information.

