3. **Triplicate 12-Lead ECG:** The Screening ECG will be a single 12-lead ECG. At all other times, at each time point, 3 consecutive 12-lead ECGs (triplicate) will be performed approximately 2 minutes apart to determine mean QTcF interval. All 12-lead ECGs should be confirmed by a qualified person at the institution. When coinciding with blood sample draws for pharmacokinetics (PK), ECG assessment should be performed prior to blood sample collection, such that the blood sample is collected at the nominal time. If the mean QTcF is prolonged (≥45 msec from the baseline or >500 msec), the ECGs should be re-evaluated by a qualified person at the institution for confirmation. Additional triplicate ECGs may be performed as clinically indicated.

SCHEDULE OF ACTIVITIES PART 1B – Combination Dose Escalation

Protocol Activity	Screening		Active 7	Freatme	nt Phase	- One Cy	vcle = 28	days		End of	Post-Treatme nt Follow-Up ²⁴	
	(≤28 days prior to			Cycle	s 1 & 2			Cycles	3+	Treatment/ Withdrawal ²³		
Visit Identifier	enrollment)	Day 1	Day	Day	Day	Day	Day	Day	D		•	
(Visit Window) ^a	1		2	7	10 ^b	15	21 ^c	1	ay 7			
Informed consent ²	X											
Medical/Oncological history ³	X											
Physical examination ⁴	X									X		
Abbreviated physical examination ⁴		X		X		X		X	X		X	
Baseline signs and symptoms ⁵		X										
Height	X											
Weight	X	X						X		X		
Vital signs ⁶	X	X^6		X		X		X^6	X	X		
ECOG Performance status ⁷	X	X						X		X	X	
Laboratory												
Hematology ⁸	X	X		X		X		X	X	X		
Blood Chemistry ⁹	X	X		X		X		X	X	X		
Coagulation ¹⁰	X	X		X		X		X		X		
Urinalysis ¹¹	X			X		X		X		X		
Viral disease screening ¹²	X											
Contraception check ¹³	X	X						X		X	X	
12-lead ECG ¹⁴	X	See Pharr	nacokine	etic, ECC	CCI		San	npling Sch	nedule	for Part 1B		
Echocardiogram ¹⁵	X							X		X		
Troponin I + BNP ¹⁶	X	X		X		X		X		X		
Alk Phos fractionation ¹⁷		X										
Registration and Treatment												
Registration ¹⁸	X											
PF-06952229 ¹⁹		Orally	✓► Orally twice daily (BID) on Days 1-7 and 15-21 of each Cycle									
Enzalutamide ¹⁹			✓▶ Orally QD as continuous daily dosing									
Tumor assessments												
CT/MRI Scans ²⁰	X		S	See footn	note for fre	equency o	f scans	-		X		

SCHEDULE OF ACTIVITIES PART 1B – Combination Dose Escalation

Protocol Activity	Screening										Post-Treatme
	(≤28 days prior to			Cycles	s 1 & 2		Cycles 3+		Treatment/ Withdrawal ²³	nt Follow-Up ²⁴	

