3.2. DLT Definition

Severity of adverse events (AEs) will be graded according to CTCAE version 5.0. For the purposes of dose escalation, any of the following AEs occurring in the first cycle of treatment (within 28 days of first dose or until the patient completes the first cycle of therapy if there are treatment delays) which are clinically significant will be classified as DLTs, unless there is a clear alternative explanation and agreed upon by investigator and sponsor (eg, clearly and incontrovertibly due to underlying disease/progression or extraneous cause) where there has been a clinically significant change from baseline:

Clinically important or persistent toxicities that are not included in the criteria below
may be considered a DLT following review by Pfizer and the Investigators. All
DLTs need to represent a clinically significant shift from baseline.

Note: Labs must be repeated for confirmation. Only the lab result requiring confirmation must be repeated, not the entire panel.

Hematologic:

Any treatment-related hematologic laboratory abnormality specifically defined as:

- Thrombocytopenia Grade 4 for ≥7 days, or Grade 3 or 4 associated with ≥ Grade 2 clinically significant bleeding or requiring platelet transfusion (for bleeding events with no grading available clinically significant bleeding is defined as required hospitalization or urgent medical intervention);
- Neutropenia Grade 4 for ≥7 days; Grade ≥3 neutropenia with infection;
- Anemia Grade 4, or Grade 3 requiring blood transfusion.

Nonhematologic:

- Grade ≥3 toxicities that are considered clinically significant;
- Alanine aminotransferase (ALT)/aspartate aminotransferase (AST) >3x the upper limit of normal (ULN) with bilirubin >2x the ULN without another explanation (eg, cholestasis) will be considered a DLT, ie, confirmed drug induced liver injury (DILI) meeting Hy's law criteria;
- Grade 3 nausea, vomiting or diarrhea that does not resolve within 4 days despite maximal supportive therapy.

Nonhematologic and Non-Hepatic:

- Any toxicity causing greater than 2 weeks of dose delay is a DLT. Note: Patients deriving clinical benefit from study treatment who experience a DLT may continue on study at a reduced dose following recovery of the AE to Grade 0-1 or baseline, only after discussion between the investigator and sponsor;
- Any toxicity preventing patients from receiving 75% of study drug during the DLT evaluation period is a DLT.

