The following AEs will not be adjudicated as DLTs:

- Any Grade 3 endocrinopathy that is adequately controlled by hormonal replacement;
- Grade 3 AE of tumor flare (defined as local pain, irritation, or rash localized at sites of known or suspected tumor);
- Any Grade 5 event clearly due to underlying disease or extraneous causes;
- Isolated Grade 3 laboratory abnormalities that are not associated with clinical sequelae and are corrected with supplementation/appropriate management within

72 hours of their onset at data cut off will not be taken into account for MTD determination including but not limited to:

- Grade ≥3 electrolyte abnormality lasting <72 hours, is not clinically complicated, and resolves spontaneously or responds to conventional medical interventions;
- Grade ≥3 amylase or lipase that is not associated with symptoms or clinical manifestations or pancreatitis.
- A patient is classified as DLT-evaluable if he/she experiences a DLT or if he/she otherwise in the absence of a DLT receives at least 75% of the planned doses of each investigational product and has received all scheduled safety assessments during the DLT window. If a patient fails to meet these criteria, he/she may be replaced.

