3.3. MTD Definition

A DLT rate of 27.5% with an equivalence interval of (22.5%, 32.5%) (note: provided the DLT rate for cardiac toxicity does not exceed 10%) will be utilized to estimate the MTD; patients will be enrolled in dose cohorts of 2-4 patients, and each patient will receive 2 courses of PF-06952229 (7 days on, 7 days off) in a 28 day cycle. Due to the discreteness of the dose levels and in the interest of the safety of patients, the estimated MTD is the highest tested dose level with DLT rate ≤ approximately 32.5%. The dose finding decision will be based on a 1-cycle (28 day) DLT observation period.

At least 6 patients have been accumulated on a dose that can be predicted to be the MTD.

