5.9.2. Anti-Diarrheal, Anti-Emetic Therapy

Primary prophylaxis of diarrhea, nausea and vomiting is not permitted in the first cycle. Primary prophylaxis in subsequent cycles is at the investigator's discretion. The choice of the prophylactic drug as well as the duration of treatment is up to the investigator with sponsor approval assuming there is no known or expected DDI and assuming the drug is not included in the Concomitant Treatment(s) section.

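### The bar on primary prophylactic G-CSF in Protocol Section 5.9.1 ends at Day 14 of Cycle 1, but DLTs are counted over the whole cycle, including a second dosing week on Days 15-21

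*Protocol*

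**What the plan says.** Section 5.9.1 of the protocol limits G-CSF as follows: "Primary prophylactic use of granulocyte-colony stimulating factors is not permitted during the first 14 days of Cycle 1". It separately allows G-CSF to treat neutropenia once it has emerged.

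The DLT window is longer. Section 3.2 counts events "within 28 days of first dose or until the patient completes the first cycle of therapy if there are treatment delays", and Section 3.3 adds: "The dose finding decision will be based on a 1-cycle (28 day) DLT observation period". The Schedule of Activities for Part 1B gives PF-06952229 as "Orally twice daily (BID) on Days 1-7 and 15-21 of each Cycle", and Section 3.3 confirms two courses per 28-day cycle.

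Neutropenia is a named DLT in Section 3.2: "Neutropenia Grade 4 for ≥7 days; Grade ≥3 neutropenia with infection". A patient without a DLT is evaluable if he or she "in the absence of a DLT receives at least 75% of the planned doses of each investigational product" and has had the scheduled safety assessments.

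The neighbouring Section 5.9.2 sets a full-cycle rule for gastrointestinal toxicity: "Primary prophylaxis of diarrhea, nausea and vomiting is not permitted in the first cycle".

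**The concern.** A bar on prophylaxis in a dose-finding trial keeps supportive care from hiding the toxicity being counted. Here the bar covers half the counting window and lapses on the day the second course starts. G-CSF given preventively from Day 15 could avert a neutropenia DLT or shorten it below the threshold, and the patient would enter the mTPI count as a non-DLT.

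Nothing else closes the gap. Section 5.7 leaves concomitant treatment to the treating physician, apart from named exclusions that do not include growth factors. The evaluability rule in Section 3.2 does not mention them. The major treatment deviations that remove a patient from the per-protocol set (Protocol Section 9.1, SAP Section 4.3) do not list them. The Section 3.2 provision for calling other important toxicities DLTs applies to events that occur, not to events that were prevented.

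The first-cycle DLT count drives every mTPI decision and the MTD in Parts 1A and 1B. The concern is with primary prophylaxis only; treatment of emergent neutropenia is a separate matter.

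**Working it through.** **Calendar check**

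| Item | Days | Source (Protocol) |
|---|---|---|
| Primary prophylactic G-CSF barred | 1-14 | 5.9.1 |
| DLT window | 1-28, longer if delayed | 3.2, 3.3 |
| PF-06952229 dosing | 1-7 and 15-21 | Schedule of Activities, Part 1B |
| GI prophylaxis barred | whole first cycle | 5.9.2 |

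Window days outside the bar: 28 − 14 = 14 of 28. Dosing days outside the bar: 7 of 14, the entire second course. These are shares of calendar time, not of DLTs.

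**The plan's own escalation figures**

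Protocol Section 9.2.2 and SAP Section 5.2.2 tabulate the chance of escalating, assuming escalation on 0/3 or 1/6:

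P = (1−p)³ + 3p(1−p)² × (1−p)³.

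At p = 0.40 this is 0.216 + 0.432 × 0.216 = 0.309, against the stated 0.31. All nine tabulated values reproduce. Table 2 and Appendix 2, however, score 1 DLT in 6 as Stay, so the illustration below uses Table 2.

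**Illustration under Table 2**

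Assumptions, none taken from the documents: true DLT rate 40%; patients independent; each Stay followed by another cohort of the same size, up to 12 patients; DLTs masked in 0%, 2% or 5% of patients, so that the observed rate p is 0.40, 0.38 or 0.35. Write q = 1 − p. Section 3.3 provides that "patients will be enrolled in dose cohorts of 2-4 patients"; sizes 3 and 4 are used, since Section 3.1.1.4 asks for at least 3 evaluable patients.

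Cohorts of 3:
- By n = 6 the only route to escalation is 0/3, so P = q³.
- By n = 12 the routes 1/9 (3pq⁸) and 2/12 (18p²q¹⁰) are added, so P = q³ + 3pq⁸ + 18p²q¹⁰.

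Cohorts of 4, by n = 12: the routes are 0/4, 1/8 and 2/12, so P = q⁴ + 4pq⁷ + 16p²q¹⁰.

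Worked case, cohorts of 3, p = 0.40, n = 12: 0.2160 + 0.0202 + 0.0174 = 0.254.

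| DLTs masked in | p | Cohorts of 3, n = 6 | Cohorts of 3, n = 12 | Cohorts of 4, n = 12 |
|---|---|---|---|---|
| 0% of patients | 0.40 | 0.216 | 0.254 | 0.190 |
| 2% of patients | 0.38 | 0.238 | 0.285 | 0.221 |
| 5% of patients | 0.35 | 0.275 | 0.338 | 0.274 |

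A single hidden event can also change a decision directly: in Table 2, 0/3 is Escalate and 1/3 is Stay.

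**The case against.** The textual gap is not in dispute; the case on the other side is that it hardly matters.

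- **Rare use.** Hematology is scheduled on Days 1, 7 and 15. If neutropenia is present by Day 15, G-CSF is treatment and already allowed. If counts are normal, an investigator has little reason to start prophylaxis. This stands and limits the size.
- **Therapeutic G-CSF stays open.** It can shorten a Grade 4 episode to under 7 days, so the fix closes only part of the route by which G-CSF can lower the DLT count. This stands; the fix should not be presented as removing all of it.
- **Sparse sampling.** No hematology is scheduled between Day 15 and Cycle 2 Day 1, so a late Grade 4 episode of 7 days might go undocumented with or without G-CSF. This also limits the size, although infection or unscheduled tests would still reveal cases.
- **No signal so far.** Appendix 10 itemises 25 Grade 3, two Grade 4 and one Grade 5 events in 20 patients, and none is neutropenia. Those data are preliminary and monotherapy only. Section 1.5 reports decreased neutrophils among the most common related events of Grade 3 or higher with galunisertib, another inhibitor of this target, so the risk cannot be dismissed at higher doses or with enzalutamide.
- **The illustration is not an error rate.** Escalating is not the same as choosing a wrong MTD: the next dose is tested under the same rules, and escalation may stop at 6-12 patients on the predicted MTD. This is correct.

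These points bear on magnitude. None supplies a reason for ending the bar halfway through the window it protects.

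**Conclusion.** The concern holds as a minor point. The mismatch between a 14-day bar and a first-cycle DLT window is certain from the text, and the direction of any bias is certain too: fewer observed DLTs and a higher dose. Its size is not known and the low end is zero. The escalation probabilities above rest entirely on the assumed 40% rate, the assumed masking shares and accrual continuing on every Stay; they show sensitivity, not an expected effect. No sample size or probability stated in the plan is wrong on this account.

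**What to change.** In Section 5.9.1, replace the 14-day limit with wording such as: *not permitted during Cycle 1 (the DLT observation period, including any extension for treatment delay)*. This matches Section 5.9.2 and follows the window in Section 3.2. Leave therapeutic use for emergent neutropenia as it is. Section 3.2 and the SAP need no change.

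The cost is that primary prophylaxis is withheld for about 14 more days, and for longer when Cycle 1 is delayed. This would also apply to the roughly 30 expansion patients (10 in Part 2A, 20 in Part 2B). If the sponsor does not want that, the longer bar can be limited to Parts 1A and 1B, bearing in mind that Section 3.1.1.4 also uses the DLT interval to monitor cohort expansion.
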